PGIC:	Patient Global Impression of Change
PK:	pharmacokinetics
PT:	preferred term
SAE:	serious adverse event
SAP:	statistical analysis plan
SD:	standard deviation
SDMT:	Symbol Digit Modalities Test
SMQ:	Standardized MedDRA Query
SOC:	system organ class
TEAE:	treatment-emergent adverse event
TMT-A:	Trail Making Tests Part A
TMT-B:	Trail Making Tests Part B
ULN:	upper limit of normal range
WHO-DD:	World Health Organization-Drug Dictionary

1 OVERVIEW AND INVESTIGATIONAL PLAN

This Statistical Analysis Plan (SAP) is intended to be a detailed description of the definitions and statistical techniques to be used for the analyses of data collected in ACT14820 study.

The first, second and third versions of this SAP covered the analyses of data collected during Part 1 of the study, and were finalized prior to the analysis of Part 1 non-Japan and Part 1 Japan data, respectively. The fourth version covered the analyses of data collected during Part 2 of the study, including the 52-week blinded treatment period (Period 2) and the 104-week duration long-term follow-up (LTFU) period (Period 3).

This SAP was amended following recommendations from the FDA to exclude data collected after treatment discontinuation from the primary analysis and use them in sensitivity analyses.

This amended SAP was finalized prior to the final analysis of Part 2 study to ensure the credibility of the study results by pre-specifying the statistical methods for analyses before unblinding of treatment assignments.

Details of amendments of the SAP are described in [Table 2](#).

1.1 STUDY DESIGN AND RANDOMIZATION

This is a two-part, multicenter, multiple-country, randomized, double-blinded, placebo-controlled study in early-stage Parkinson Disease (PD) patients carrying a GBA mutation. The study will be divided into 2 consecutive parts. Part 1 will be a randomized, double-blinded, placebo-controlled dose escalation study, utilizing a sequential cohort design. Part 1 will allow selection of the dose of GZ/SAR402671 for Part 2, a randomized, double-blind, placebo-controlled, 2-arm study of the efficacy and safety of GZ/SAR402671. Part 1 will be conducted only in selected sites (approximately 20 sites [including 4 Japanese sites]); Part 2 will be conducted at multiple sites (approximately 50). Part 2 will start after the appropriate dose for Part 2 is selected in Part 1.

In Part 1, during the screening/baseline period, from Day -60 to Day -1, patients will provide informed consent and undergo screening assessments to determine trial eligibility and undergo baseline measurements. If all eligibility criteria are met, patients will enter the trial. Part 1 will determine the safety and tolerability of GZ/SAR402671 at 4, 8, and 15 mg in early-stage PD patients carrying a GBA mutation by using a dose escalation scheme (4 weeks to assess safety and tolerability of dose and a minimum of an additional 4 weeks to further assess safety and tolerability and any potential changes in other exploratory endpoints in each dose cohort). There will be 3 sequential cohorts that will be placebo-controlled:

- Cohort 1: 4 patients (or 3 patients in Japan) on GZ/SAR402671 4 mg and 1 patient on placebo
- Cohort 2: 4 patients (or 3 patients in Japan) on GZ/SAR402671 8 mg and 1 patient on placebo

- Cohort 3: 4 patients (or 3 patients in Japan) on GZ/SAR402671 15 mg and 1 patient on placebo

No additional dose escalation of GZ/SAR402671 will occur above the highest proposed dose of 15 mg. All patients must complete the first 4 week course of therapy with subsequent blinded data review by an internal review committee whose purpose is to review blinded data (such as safety, tolerability, and/or relevant clinical endpoints), demonstrating safety/tolerability before dose escalation to the next higher level can occur. Patients will continue to be dosed daily and will be followed every 4 weeks until the completion of Part 1, allowing for additional safety and other exploratory endpoints to be collected. Each cohort will have a 4:1 randomization ratio, and the total sample size will be approximately 15 patients (including 12 on GZ/SAR402671 and 3 on placebo). In Japan, each cohort will have a 3:1 ratio, and the total sample size will be approximately 12 Japanese patients (including 9 on GZ/SAR402671 and 3 on placebo). Therefore, the total sample size in Part 1 will be approximately 27 patients.

At the end of 4 weeks of treatment during the dose escalation part, patients in each cohort will have a lumbar puncture (LP); CSF exposure of GZ/SAR402671 will be measured at 2 time points in Part 1: at pretreatment and Week 4. If there is no CSF exposure at the highest dose level, the study will be stopped.

In Part 2, the GZ/SAR402671 dose will be the highest dose determined to be safe and well tolerated in Part 1. Moreover, CSF exposure must be known. If there is no CSF exposure of GZ/SAR402671, then that dose will not be used in Part 2.

If patients from Part 1 continue to meet eligibility requirements, and are willing to continue in the study, they may enroll in Part 2, but re-randomization will be required; furthermore, they will have to sign another informed consent form. All screening assessments will need to be repeated, except for the genetic screening, magnetic resonance imaging (MRI), LP, and ioflupane I-123 injection DaTSCAN (DaTSCAN), to confirm eligibility of patients from Part 1 to enroll in Part 2.

In Part 2, eligible patients will be stratified based on use of levodopa/PD medication (yes/no), cognitive function (Montreal Cognitive Assessment [MoCA] score <26 [yes/no]) and severe GBA mutation (yes/no). Patients will be randomized in a 1:1 ratio to receive GZ/SAR402671 or placebo for 52 weeks.

Part 2 will include 4 main periods: the up to 60-day screening period (Period 1), the 52-week blinded treatment period (Period 2), the 104-week duration long-term follow-up (LTFU) period (Period 3), and the 6-week post treatment observation period (Period 4).

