1.2 OBJECTIVES

1.2.1 Part 1: Dose escalation phase

1.2.1.1 Primary objectives

To determine the safety and tolerability of 4, 8, and 15 mg of GZ/SAR402671, as compared to placebo, when administered orally daily for 4 weeks in early-stage PD patients carrying a GBA mutation or other prespecified sequence variants (from now on both mutation types are referred to as ‘GBA mutation’). This will allow selection of the dose for the second part of this study (this does not apply to Japanese patients).

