All safety analyses will be performed using the following common rules:

- Safety data in patients who do not belong to the safety population (eg, exposed but not randomized) will be listed separately.
- The baseline value is defined in [Section 2.1.1](#)
- The potentially clinically significant abnormality (PCSA) values are defined as abnormal values considered medically important by the Sponsor according to predefined criteria/thresholds based on literature review and defined by the Sponsor for clinical laboratory tests, vital signs, and ECG (PCSA version dated 24 May 2014 [[Appendix A](#)])
- PCSA criteria will determine which patients had at least 1 PCSA during the TEAE period, taking into account all evaluations performed during the TEAE period, including unscheduled or repeated evaluations. The number of all such patients will be the numerator for the on-treatment PCSA percentage

- The treatment-emergent PCSA denominator by arm for a given parameter will be based on the number of patients assessed for that given parameter in the TEAE period by treatment arm on the safety population
- For quantitative safety parameters based on central laboratory/reading measurements, descriptive statistics will be used to summarize results and change from baseline values by time point and treatment arm. Summaries will include the endpoint baseline value, the last on-treatment value and change from baseline, the worst on-treatment value and change from baseline. The last on-treatment value is commonly defined as the last value collected during the treatment period (see [Section 2.1.4](#)). The worst on-treatment value is defined as the nadir and /or the peak post-baseline during the treatment period according to the direction (minimum or maximum) of the abnormality as defined in the PCSA list
- All measurements (scheduled or unscheduled) will be re-allocated as given in [Section 2.5.4](#), [Table 3](#) and [Table 6](#) and re-allocated visits measurements will be included in the by-time point summary
- The analysis of the safety variables will be essentially descriptive and no systematic testing is planned

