2.4.5.1 Analyses of adverse events

Generalities

The primary focus of AE reporting will be on TEAE as defined in [Section 2.1.4](#). Pre-treatment and post-treatment adverse events (including SAEs and AESIs) will be described separately.

If an AE date/time of onset (occurrence, worsening, or becoming serious) is incomplete, an imputation algorithm will be used to classify the AE as pre-treatment, treatment-emergent, or post-treatment. The algorithm for imputing date/time of onset will be conservative and will classify an AE as treatment emergent unless there is definitive information to determine it is pre-treatment or post-treatment. Details on classification of AEs with missing or partial onset dates are provided in [Section 2.5.3](#).

Adverse event incidence tables will present by SOC, HLGT, HLT, and PT, for each treatment arm, the number (n) and percentage (%) of patients experiencing an AE sorting based on results of column all. Multiple occurrences of the same event in the same patient will be counted only once in the tables within a treatment period. The denominator for computation of percentages is the safety population within each treatment arm.

Sorting within tables ensures the same presentation for the set of all AEs within the observation period (pre-treatment, treatment-emergent, and post-treatment). For that purpose, the table of all TEAEs presented by SOC and PT sorted by the internationally agreed SOC order and decreasing frequency of PTs within SOC will define the presentation order for all other tables unless otherwise specified. Sorting will be based on results of column all.

Analysis of all TEAEs

The following TEAE summaries will be generated for the safety populations.

- Overview of TEAEs by treatment arm, summarizing number (%) of patients with any
 - TEAE
 - Serious TEAE
 - Treatment-emergent AESI
 - TEAE leading to death
 - TEAE leading to permanent treatment discontinuation
- All TEAEs by primary SOC, HLGT, HLT, and PT, showing number (%) of patients with at least 1 TEAE sorted by the SOC internationally agreed order. The other levels (HLGT, HLT, and PT) will be presented in alphabetical order. This table will be presented by treatment arm

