3 INTERIM ANALYSIS

Different data review and interim analyses will be performed during the conduct of Part 1 of the study.

3.1 INTERNAL DATA REVIEW PRIOR TO DOSE ESCALATION IN PART 1

An internal review committee will perform safety data review after the completion of 4 weeks of dosing in all patients from non-Japanese Cohort 1 prior to dosing of the subsequent cohort; the same process will be repeated after the completion of 4 weeks of dosing in all non-Japanese patients in Cohort 2. Review of blinded safety data from Japanese patients in Cohort 1 and Cohort 2 will follow the same process and will be performed separately. Specifically, the internal review committee will review the AE/SAE data and other available individual patient safety data from all the patients in each cohort in a blinded fashion. No additional dose escalations will occur above the highest proposed dose of 15mg. No dose escalation may occur until the last patient in a given cohort has completed 4 weeks of administration of IMP.

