3.5 GENERAL CONVENTIONS FOR INTERIM ANALYSES

Analyses methods and conventions described in the other sections of this SAP will be applied for all data reviews and interim analyses as applicable. The following additional rules will apply for data reviews and interim analyses:

- Patients without end of treatment visit performed at the time of the cut-off date will be considered as ongoing and exposed up to the cut-off date. Therefore:
 - Patients who did not complete treatment period nor prematurely discontinued the study treatment at cut-off date will be analyzed as “ongoing” in the disposition summary
 - Their TEAE period, treatment period and on-study observation period will end at the cut-off date
 - Their treatment duration will be derived by considering date of cut-off as last IMP dose date
- Analyses of compliance will be performed up to the last IMP dose reported in the e-CRF up to the cut-off date
- AEs occurring, worsening or becoming serious after the cut-off date will not be included in the analyses. However, any available outcome of an adverse event starting prior to the cut-off date will be taken into account, including outcomes posterior to the cut-off date
- Any safety assessment (including physical examination, neurological examination, ophthalmological examination, clinical laboratory evaluations, vital signs, ECG) performed after the cut-off date will not be included in the analyses
- Medications, treatment discontinuations/completions and deaths occurring after the cut-off date will not be included in the analyses
- Post-treatment period, post-study period are not applicable for ongoing patients. Analyses of post-treatment AEs, post-study deaths and post-treatment medications will be performed for patients who either completed or prematurely discontinued the treatment before or at the cut-off date
- Patients will be considered alive at the cut-off date, unless death before the cut-off date has been reported

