2. BACKGROUND

Study design:

ACT14820 is a two-part, multicenter, multiple-country, randomized, double-blinded, placebo-controlled study in early-stage PD patients carrying a GBA mutation.

The study will be divided into 2 consecutive parts.

Part 1 will be a randomized, double-blinded, placebo-controlled dose escalation study, utilizing a sequential cohort design. Part 1 will allow selection of the dose of GZ/SAR402671 for Part 2. There will be 3 sequential cohorts that will be placebo-controlled:

- Cohort 1: 4 patients on GZ/SAR402671 4 mg and 1 patient on placebo
- Cohort 2: 4 patients on GZ/SAR402671 8 mg and 1 patient on placebo
- Cohort 3: 4 patients on GZ/SAR402671 15 mg and 1 patient on placebo

All patients must complete the first 4 week course of therapy with subsequent data review, demonstrating safety/tolerability before dose escalation to the next higher level can occur. Patients will not escalate to a higher dose during Part 1. No additional dose escalation of GZ/SAR402671 will occur above the highest proposed dose of 15 mg.

In Japan, each cohort will have a 3:1 ratio, and the total sample size will be approximately 12 Japanese patients (including 9 on GZ/SAR402671 and 3 on placebo):

- Japanese Cohort 1: 3 Japanese patients on GZ/SAR402671 4 mg and 1 Japanese patient on placebo
- Japanese Cohort 2: 3 Japanese patients on GZ/SAR402671 8 mg and 1 Japanese patient on placebo
- Japanese Cohort 3: 3 Japanese patients on GZ/SAR402671 15 mg and 1 Japanese patient on placebo

Part 2 will be a randomized, double-blinded, placebo controlled, 2-arm study. Part 2 will start after the appropriate dose for Part 2 is selected, following the review of data from Part 1 in non-Japanese patients.

Data reviews and interim analyses:

Different data review and interim analyses will be performed during the conduct of the study:

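### Part 1 safety percentages mix unequal follow-up across doses, so they tend to understate risk at 15 mg relative to 4 mg, and none matches the 4-week primary objective

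*SAP*

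**What the plan says.** Section 1.1 of the SAP sets the design: "There will be 3 sequential cohorts that will be placebo-controlled", at 4, 8 and 15 mg in that order. Section 3.1 sets the gap between cohorts: "No dose escalation may occur until the last patient in a given cohort has completed 4 weeks of administration of IMP". Appendix K, under Background, adds that "Patients will not escalate to a higher dose during Part 1". Each cohort has 4 weeks of treatment and then at least 4 more, but the end of dosing is shared (Section 1.1): "Patients will continue to be dosed daily and will be followed every 4 weeks until the completion of Part 1".

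The Part 1 primary objective (Section 1.2.1.1) is safety and tolerability of the three doses "as compared to placebo, when administered orally daily for 4 weeks in early-stage PD patients carrying a GBA mutation". Section 2.1.3.1 names the safety of each dose cohort as the primary endpoint.

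The counting rules are these:
- The treatment-emergent period runs from first dose to 6 weeks after last dose (Section 2.1.4).
- For adverse events, "The denominator for computation of percentages is the safety population within each treatment arm" (Section 2.4.5.1).
- For laboratory, vital-sign and ECG abnormalities, "PCSA criteria will determine which patients had at least 1 PCSA during the TEAE period" (Section 2.4.5).
- New eye findings (Section 2.4.5.8) and the worst BDI-II category (Section 2.4.5.9) are taken over the same whole period.
- At data reviews, for ongoing patients, "Their TEAE period, treatment period and on-study observation period will end at the cut-off date" (Section 3.5).

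Patient-years are reported in Section 2.4.3.1 as a description of exposure. No event table uses them.

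**The concern.** A patient in the 4 mg cohort is watched for longer than a patient in the 15 mg cohort, because the first cohort waits while the later ones open and all finish together. The chance of at least one event at any time grows with time watched. The crude percentage at 4 mg is therefore raised relative to 15 mg even if the doses are equally safe. A modest real increase in risk at 15 mg can be hidden, or an inverse dose trend can appear, in tables that Section 3.4 says are intended for publication. The objective also asks about 4 weeks of dosing, and no planned incidence table answers that question.

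**Working it through.** **The plan's own figure.** Part 1 size: 3 × (4 + 1) = 15 non-Japanese and 3 × (3 + 1) = 12 Japanese patients, 27 in total, as stated. The SAP gives no event rate and no follow-up time per cohort for Part 1.

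**Follow-up per cohort.** Inputs are the 4-week wait between cohorts (Section 3.1), at least 8 weeks of dosing in each cohort (Section 1.1), a shared end (Section 1.1) and the 6-week residual period (Section 2.1.4). Review and enrolment time between cohorts is set to zero.
- Dose-selection snapshot, when the last cohort has 4 weeks and follow-up stops at the cut-off: 4 + 4 + 4 = 12, 4 + 4 = 8, and 4 weeks. Ratio of 4 mg to 15 mg: 12/4 = 3.
- Final Part 1 tables: 16, 12 and 8 weeks on drug, plus 6 each, gives 22, 18 and 14 weeks. Ratio: 22/14 = 1.57.

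The times are minima; the ratios are not bounds. If cohort 1 reached 36 weeks on drug (the top Part 1 exposure category in Section 2.4.3.1), 4-week gaps would give 42, 38 and 34 weeks with the residual period, ratio 1.24. With 8-week gaps it would be 42, 34 and 26 weeks, ratio 1.62.

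**Expected crude percentages with no dose effect.** Formula: 100 × [1 − exp(−h × weeks)]. The hazard h is an assumption, constant and equal at all doses. Percentages are in the order 4/8/15 mg.

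| h per patient-week | Snapshot, 12/8/4 weeks | Final tables, 22/18/14 weeks | First 4 weeks, every dose |
|---|---|---|---|
| 0.01 | 11.3/7.7/3.9 | 19.7/16.5/13.1 | 3.9 |
| 0.02 | 21.3/14.8/7.7 | 35.6/30.2/24.4 | 7.7 |
| 0.05 | 45.1/33.0/18.1 | 66.7/59.3/50.3 | 18.1 |
| 0.10 | 69.9/55.1/33.0 | 88.9/83.5/75.3 | 33.0 |

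**What it takes to overcome the imbalance.** Crude percentages at 4 and 15 mg are equal when the hazard ratio equals the follow-up ratio, about 1.57 in the final tables. At 0.05 per week, a true 1.5-fold hazard at 15 mg gives 1 − exp(−0.075 × 14) = 65.0%, still below the 66.7% at 4 mg. A true doubling gives 75.3% against 66.7%: the right direction, but compressed. Over the first 4 weeks the same doubling would show as 33.0% against 18.1%.

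**Chance.** With 4 patients per dose, equal hazards and 22/18/14 weeks, the 15 mg count falls below the 4 mg count with probability 0.40 to 0.55 over the four hazards, and above it with probability 0.15 to 0.23. It is strictly the lowest of the three with probability 0.18 to 0.35.

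**Placebo.** Each cohort has one placebo patient. If placebo is pooled across cohorts (an assumption), its mean follow-up is (22 + 18 + 14)/3 = 18 weeks against 14 at 15 mg, so that contrast leans the same way.

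**The case against.** Much of the case on the other side stands. Part 1 is small, unpowered and descriptive, with no dose-trend test. Quantitative laboratory, vital-sign and ECG values, and the BDI-II total, are also summarised by time point, which does align the doses. Exposure by arm is tabulated, so a careful reader can see the imbalance. With about 27 patients, individual listings can be read. What remains uncorrected is the incidence tables: adverse events, adverse events of special interest, PCSAs, eye findings and worst BDI-II.

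A reader might infer that 15 mg will look safest. The documents do not support that as a statement of fact. The tilt is in expectation, and with 3 or 4 patients per dose the observed order can easily go the other way. The tilt is also smaller for events that occur early in treatment.

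A reader might also infer that the Part 2 dose choice is unsound. That does not follow either. The 3-to-1 follow-up ratio belongs to the dose-selection snapshot only, and that review is past: this version of the SAP already specifies 15 mg for Part 2 (Sections 2.4.3.2 and 2.4.4). Escalation rested on blinded individual patient data, and the Part 2 dose was to be the highest judged safe and tolerated, not the one with the lowest percentage.

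Finally, the any-time tables should not be demoted. Section 1.1 keeps patients on drug beyond 4 weeks partly to learn more about safety, and late events such as lens opacities may appear only there.

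**Conclusion.** The concern holds as a limited reporting flaw. The SAP's own rules make follow-up shorter at higher doses, and no incidence table corrects for it or matches the 4-week objective. In the final Part 1 tables, minimum follow-up is about 22, 18 and 14 weeks. An assumed equal hazard of 0.05 per week turns that into about 67%, 59% and 50% with no dose effect. The follow-up times are derived from the SAP with no delay between cohorts. The hazard and its constancy are assumptions, and the ratio moves with the actual gaps and the actual length of Part 1. The consequence is for how the Part 1 tables are read, not for the dose decision.

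**What to change.** In Section 2.4.5, for Part 1, keep the any-time tables and add beside them:
- Incidence tables for adverse events, adverse events of special interest, PCSAs, eye findings and worst BDI-II, limited to each patient's first 4 weeks of dosing, to match the primary objective.
- The same tables for the first 8 weeks among patients with that exposure. Show beside them the number who stopped earlier and their events, so that stopping for an adverse event does not remove the event from view.
- Events per patient-year by dose, with the time at risk defined over the same period in which events are counted.

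State that doses are to be compared on the common-period tables, and that the any-time tables describe the full experience. Leave the completed end-of-Part-1 review unchanged. The SAP's history (Section 1.6) places the Part 1 analyses before this version, so label the additions as supplementary.

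The cost is a few extra tables from data already collected. Counts in the 4-week set will be sparse: at 18.1%, 4 patients give 0.72 expected with an event. An eye finding can enter only if an examination falls within the period.

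No change to conduct or to any clinical rule is involved.
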